Once patients have consented to participation, subjects will be randomly assigned to either intervention or control group-both consisting of 22 patients. Consent will be obtained by referring physicians, or physical therapists at approved sites participating in the study [further details regarding consent procedure below]. At all physical therapy sites participating in the study, patient service representatives will be trained in the study recruitment, collecting patient enrollment paperwork and other clerical needs. Allocation will occur in blocks of 4 by opaque envelope. The envelopes will be generated by web based randomization software²¹ placed into opaque, sequentially numbered envelopes and delivered to participating physical therapy clinics prior to beginning recruitment. Two sites will contain 4 blocks of 4 envelopes, and one site will contain 3 blocks of 4, ensuring a total of 44 patients. If one site or another enrolls more patients, only a full block of 4 envelopes will be transferred to that site for further enrollment. The envelopes will be stored in the desk of the directing physical therapist at each location,

and only removed once a patient has been enrolled. Once patients consent to enroll in the study, they will receive the next envelope in sequence in the group of 4, and be allocated to either the intervention or control group. The envelope will contain a number which the treating physical therapist will then compare to the master allocation list, which will reveal which treatment group #1 or #2(intervention or control) the patient has been allocated; it will also contain the patient's assigned identification number (PID). The treating physical therapist will be responsible for communicating the subject's allocation and PID which will be contained in their envelope to the primary investigator, who will hold the confidential master list. Outcomes data will be collected in a separately in REDCap.

Blinding

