Patients and treating therapists will be aware of the treatment rendered. Patients will self-enter their answers on the PRTEE and NPRS at the first, and 6th or final physical therapy visit. This data will either be self-entered to REDCap website, or onto paper copy which will be entered into REDCap by researcher blinded to their allocation. The treating physical therapists will be blinded to these results. Grip strength, and maximum pain free grip will be recorded at each therapy visit by treating physical therapist who is not blinded to the treatment allocation. We have made this decision understanding the risk of biasing a secondary outcome, but the burden of having multiple therapists at each site accommodate the institutional expectations for participating in research in order to have blinded assessment, has made this a necessity. Post treatment assessment with the NPRS and the PRTEE will be done via online REDCap survey. A researcher blinded to allocation will be responsible for contacting patients not responding to email contact to request completion of the online survey. A separate researcher, blinded to group allocation will analyze the final results that will be stored in REDCap.

Device

We will be using the Delfi personalized tourniquet system for BFR in this study (Delfi Medical Innovations Inc., [name]). The Delfi system allows a specific limb occlusion pressure to be applied to a patient's limb in order to reduce their arterial flow by a proscribed amount. In our project, we will use 50% occlusion as the standard ²².

Physical therapy staff participating in the study will be trained on the use of BFR technology. At least one therapist will attend formal training provided by the device developer prior to beginning enrollment in the study. After receiving training, all other participating therapists will be trained by the therapist/s who have received formal training.

Statement from the manufacturer (received via email):

The Delfi PTS Personalized Tourniquet System for BFR device when used according to the device's Intended Use and Indications for Use statements in the Operator and Maintenance Manual is cleared for market under Delfi Medical Innovations Inc.'s FDA Device Listing for Pneumatic Tourniquets E127474 as a Class I device exempt from premarket notification procedures. Delfi Medical Innovations Inc. is a registered establishment with the FDA under registration number 9681444.

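### A single known block size of 4 at open-label sites lets a recruiter who knows the block's history foresee, on average, one assignment in three

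*Combined protocol and SAP*

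**What the plan says.** All references are to the combined protocol and SAP.

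- **Randomization/Allocation, block size:** "Allocation will occur in blocks of 4 by opaque envelope". This is the only size given.
- **Same section, numbers:** "subjects will be randomly assigned to either intervention or control group-both consisting of 22 patients", and "Two sites will contain 4 blocks of 4 envelopes, and one site will contain 3 blocks of 4, ensuring a total of 44 patients".
- **Same section, handling:** "The envelopes will be stored in the desk of the directing physical therapist at each location". After consent, "they will receive the next envelope in sequence in the group of 4". If a site over-recruits, "only a full block of 4 envelopes will be transferred to that site for further enrollment".
- **Same section, consent:** "Consent will be obtained by referring physicians, or physical therapists at approved sites participating in the study".
- **Blinding:** "Patients and treating therapists will be aware of the treatment rendered".

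The stated safeguards are opaque, sequentially numbered envelopes that are taken out only after enrolment, and the statement under Confidentiality of Data that those who enrol or consent patients cannot see group membership.

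**The concern.** Concealment fails when the person deciding whether and when to enrol a patient can work out the next assignment. Three things come together here: the block size is fixed and written down, the block boundaries can be followed because envelopes are used and moved in fours, and past assignments are known because treatment is open. Brief Design Description has one therapist per site trained in delivery and data collection, so the same person probably sees most of a site's assignments. Opaque envelopes do not help, because the inference is made from past assignments and no envelope has to be opened.

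A site therapist who can predict can also act. Therapists may take consent. Under Inclusion / Exclusion Criteria, referral diagnoses other than lateral epicondylitis or tennis elbow are confirmed at the first therapy visit on clinical signs. Selective or delayed enrolment would make the arms differ at entry, in a trial of 44 patients with a self-reported primary outcome.

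**Working it through.** **Inputs.** Block size 4; 4 + 4 + 3 blocks over three sites; 22 per arm (all from Randomization/Allocation). The 2:2 split within blocks is not stated; it is the standard reading of 11 blocks giving 22:22.

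**The plan's own figure.** (4 + 4 + 3) × 4 = 44. It reproduces.

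**Certain assignments.** A 2:2 block has C(4,2) = 6 equally likely sequences. An assignment is certain once one arm has filled its two places.

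| Position | Chance that it is certain | Chance that the best guess is right |
|---|---|---|
| 1 | 0 | 1/2 |
| 2 | 0 | 2/3 |
| 3 | 2/6 = 1/3 (first two match) | 1/3 × 1 + 2/3 × 1/2 = 2/3 |
| 4 | 1 | 1 |
| Sum per block | 4/3 | 2.833 |

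- Share certain: (4/3)/4 = 33.3%.
- Over 11 completed blocks: 11 × 4/3 = 14.7 of 44. By site: 5.3 of 16, 5.3 of 16 and 4.0 of 12.
- Each block yields one or two certain assignments, so the range is 11 (25%) to 22 (50%).
- Best guessing is right for 2.833/4 = 70.8%, against 50% if assignments were unpredictable.

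**Possible bias.** Let d be the PRTEE points by which steering shifts the expected change of an enrolled patient, upward when one arm is foreseen and downward when the other is. The documents give no d; 1 to 3 is an assumed range. The bias in the treatment difference is 2d × (mean agreement between guess and assignment), where agreement is +1 if right, −1 if wrong and 0 if no guess is acted on.

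- Only certain assignments steered: 2d × (4/3)/4 = 0.67d, or 0.7 points at d = 1 and 2.0 at d = 3.
- Every non-tied guess steered: agreement per block is 0 + (2/3 − 1/3) + 1/3 + 1 = 5/3, so 2d × (5/3)/4 = 0.83d, or 0.8 points at d = 1 and 2.5 at d = 3.
- Nobody acts: zero.

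**Effect of hiding and varying the block size.** Simulation, 10,000 runs of 16 patients. The recruiter knows which sizes are possible and the full history, but not the size of each block. With p the best-guess rate, the last column is 2(2p − 1)d.

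| Scheme | Certain | Best guess right | Bias, certain only | Bias, every non-tied guess |
|---|---|---|---|---|
| Fixed 4 | 33.3% | 70.8% | 0.67d | 0.83d |
| Hidden 4/6 | 5.9% | 68.4% | 2 × 0.059d = 0.12d | 0.74d |
| Hidden 2/4/6 | 3.6% | 69.5% | 2 × 0.036d = 0.07d | 0.78d |

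**The case against.** **The recruiter may not know the history.** Recruitment/Enrollment gives first contact and scheduling to a consent team, referring physicians may also take consent, and Confidentiality of Data keeps group from those enrolling. For such recruiters the one-in-three figure need not apply. This stands as a limit on scope. It does not remove the point, because Randomization/Allocation lets site therapists consent patients and has the treating therapist look up the allocation. The two sections cannot both hold for a therapist who does both.

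**Steering on the primary measure is limited.** The Blinding section keeps PRTEE and NPRS results from treating therapists, and Statistical Analysis plans a regression on age, sex, symptom duration, treatments and occupation. Both bear on how large d could be. Neither prevents selection on what a therapist sees at the first visit.

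**A reader might infer a bias of about 2.5 points, a quarter of the 10-point target.** The documents do not support that as an expectation. It needs d = 3, which puts patients enrolled under opposite guesses 6 points apart (0.6 of the planning SD of 10), and it needs every non-tied guess to be acted on, including position 2, which is never certain.

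**A reader might also infer that envelopes are bundled by block.** The text implies that boundaries can be followed on site but does not describe the packaging.

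**Varying the block size does little against guessing.** This stands: guessing the arm that is behind needs no knowledge of block size.

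**The master list may be a larger gap.** The treating therapist compares the envelope number with a master list that the primary investigator is said to hold. If a copy is at the site, more than a third of assignments could be exposed. The documents leave this open, so the fix has to cover it.

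**Conclusion.** The point holds as a design weakness worth correcting. With one known block size of 4 and open treatment, a recruiter who knows the current block's history can foresee with certainty one assignment in three on average: 14.7 of 44, never fewer than 11 or more than 22 if all blocks are completed. Unfinished blocks would lower the count. The result rests on the inferred 2:2 split and on the recruiter knowing the earlier assignments, which is well supported for site therapists and less so for referring physicians or the consent team.

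The resulting bias cannot be estimated from the documents. It runs from zero, through 0.7 to 2.0 points if only certainties are steered, to 0.8 to 2.5 points if every non-tied guess is, for an assumed d of 1 to 3. Nothing in the plan shows that anyone would steer enrolment.

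**What to change.** 1. Release each allocation centrally, only after consent and eligibility are irrevocably recorded, and keep no allocation list at the site. REDCap already holds the trial data and could do this. The documents do not say whether its randomisation function is available; release by someone outside the sites who does not recruit would also serve.
2. Generate the site-stratified sequence with randomly varying block sizes (for example 4 and 6), keep the sizes out of site documents, and do not group allocations by block. If a site over-recruits, extend its sequence centrally. Adding size 2 lowers certainty a little further (about 4% against 6%) but makes guessing slightly easier (69.5% against 68.4%).
3. Reconcile Confidentiality of Data with Randomization/Allocation: state who may consent patients, who learns the allocation and when.

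**Cost.** One new list and a central release step. Final totals may differ slightly from 22/22: an unfinished block of 6 leaves one arm ahead by at most 3 at a site, against 2 for an unfinished block of 4. Guessing from past assignments remains possible, and the report should say so. If recruitment has begun, apply the change to unused blocks and report the limitation for the rest.

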This will be a randomized, controlled, open label trial. A total of 44 subjects will be recruited. Each group will be divided equally with 22 subjects having been diagnosed with lateral elbow pain. Subjects will be recruited from CCAG physicians located within the CCAG health system, as well as at physical therapy locations at Health and Wellness Centers in Bath, Green, and Stow. A team of physical and occupational therapists have been recruited including therapists and athletic trainers who are present at each office. At each site, 1 therapist will undergo a 2 hour standardized training session on delivery of treatment and data collection. Patients evaluated and found to have the appropriate criteria by either physicians or physical therapists will be given a research information sheet (see appendix) offering the opportunity to participate in a research study at the above mentioned locations. The patients interested will be consented by phone, or in person once they present to physical therapy office.

Timeline of Study

The goal is a 6-week treatment period at 1 PT visit per week. In ideal situation the visits occur in consecutive weeks, but will be considered per protocol with 6 visits over a 12 week period. Follow up will occur for 12 months after the initial therapy visit. We anticipate the total open period of time to last between 2-3 years for completion of 1 year follow up, 2019-2022.

- A patient can elect to drop from the study at any time.
- A patient's treatment will be considered completed if they cannot attend 6 visits within the 12 week time frame.
- A patient can be discharged from care prior to 6 weeks if all clinical goals set at the initial therapy assessment are met. If this occurs the outcomes measures expected at the 6th visit will be recorded at this visit and considered equivalent to the 6th visit outcomes.

Recruitment/Enrollment

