We expect to have patients referred by doctor's offices via secure Cleveland Clinic intra-office email, by phone from doctor's offices, or by receptionists at physical therapy flagging the new patients with the eligible diagnoses. Our certified athletic trainer ([name]) or physical therapist ([name]), or summer research assistant/fellow (consent team) will make contact either ahead of the visit, or at the initial physical therapy visit to discuss the existence of the trial. One of the consent team will be responsible for initial contact with the patient, and for scheduling the consent appointment. Once the patient has expressed interest in the study, they will be met either in person at the office, or over the phone by either one of the consent team named above or IRRB approved participating physical or occupational therapists. At the office, or phone appointment, the details of the study and consent will be verbally communicated to the patient. Patients who express willingness to participate will sign the consent form at the face to face visit either after face to face conversation, or after phone conversation.

Consent will include discussing the study protocol and the perceived risks and benefits of participation. This will be done by phone with study personnel prior to, or at initial physical therapy visit. The patient will then sign a paper consent form at the therapy visit in which they enroll. The intervention treatment will be described as an experimental technique which has shown to be beneficial and safe in other therapeutic treatment protocols, but which is new to this particular diagnosis. Consent will also include patient's freedom to decline the invitation to participate, as well as a discussion of the costs associated, and the billing of their therapy in the usual manner (copays, billing insurance, etc.).

The consent forms will be held in a locked cabinet by the certified athletic trainer until turned over to study author [name] at the Bath Health and Wellness physical therapy office, where they will be stored in a locked office.

Randomization/Allocation

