Inclusion / Exclusion Criteria:

Included

The diagnoses included are lateral elbow pain, lateral epicondylitis, or lateral epicondylalgia, more general diagnoses elbow tendinitis or elbow pain will be included if their clinical picture at physical therapy meets criteria for lateral epicondylitis. If the inclusion diagnosis is other than lateral epicondylitis or tennis elbow, we will confirm the diagnosis at the first therapy visit with tenderness at the lateral epicondyle and/or pain with resisted wrist/long finger extension at the lateral epicondyle. All participants must be between the age of 18 and 70 years old and have had pain for 4 weeks or more.

Excluded

Patients presenting with a ligamentous elbow sprain, osteoarthritis of elbow and cervical radiculopathy in the affected limb will be excluded from the study. Other exclusion criteria would be inability to consent, any history of ligamentous, bony or other soft tissue reconstruction surgery at the affected elbow, history of DVT, history of endothelial dysfunction, peripheral vascular disease, pregnancy, surgical procedure on their contralateral extremity, active infection, injection therapy (corticosteroid, platelet rich plasma, or other injection therapy) in the prior 3 months to the affected site, and cancer; any surgery on affected arm in last 1 year; current fracture in affected arm; history of crush injury to affected arm; history of lymphectomy (such as axillary exploration with breast surgery, lymph node biopsy in the affected axilla/arm), sickle cell anemia or trait; kidney dialysis; history of syncope/passing out with pressure to body (such as massage, or blood pressure cuff).

Assessment of Resources:

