All patient data for research purposes will be recorded digitally in the Cleveland Clinic HIPAA compliant REDCap database. Treatment records of the patient encounters with PT will be recorded as usual in electronic health record. Hard copies of consent forms will be kept in file in locked office with athletic trainer ([name]) at Bath physical therapy office.

Confidentiality of Data

The data will not be disseminated outside of the institution. All researchers will be working within secure Cleveland Clinic networks, or via CCAG encrypted computers via VPN access when off campus. When enrolled, patients will be assigned a subject number, a master list will be kept by researcher enrolling/consenting patients in REDCap. All research data will be recorded with this subject number rather than patient identifier data. All researchers participating in the study will access to secure online databases. Enrolling/consenting research and Blinded assessor will not have access to which groups patients are enrolled in.

Plan for Record Retention and disposal

Records will be kept in REDCap until study completion. Patient identification data will be purged after the completion of data collection. The de-identified data will be kept indefinitely.

Limits to Confidentiality

Confidentiality will only be broken in the setting of a medical emergency at clinical visit, or if contacted by an outside medical provider for an emergency.

Potential Limitations of Study

Primary concerns about the study involve recruitment, and enrolling 44 patients, and following them to completion. This is a large number of lateral epicondylitis patients, and while we expect to enroll this amount, we do have a concern about doing so within two years.

There is a concern that the interpretation of results may receive criticism that the load of strengthening exercise differs between the two groups at their physical therapy visits (high load exercise in control group, low load with BFR in the intervention group). It is our goal to make clear that the intervention being tested is low load exercise in the presence of blood flow restriction together, rather than simply low load therapeutic exercise. This will be communicated in the results/discussion section of any manuscript generated. We will also make clear that both groups received the same instructions for home exercise

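### Allocation concealment is not assured: the treating therapist decodes each envelope against the master list, may also enrol patients, and need not finish baseline before the arm is revealed

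*Combined protocol and SAP*

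**What the plan says.** **Who enrols.** Randomization/Allocation states: "Consent will be obtained by referring physicians, or physical therapists at approved sites participating in the study". Recruitment/Enrollment adds that the consent discussion may be held by "either one of the consent team named above or IRRB approved participating physical or occupational therapists".

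**Who decodes.** Envelopes are opaque, sequentially numbered, sent to the clinics before recruitment and kept in the directing therapist's desk. On opening, "The envelope will contain a number which the treating physical therapist will then compare to the master allocation list", and this shows the group. The therapist then reports the allocation and PID to the "primary investigator, who will hold the confidential master list".

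**Who may know.** Confidentiality of Data says: "Enrolling/consenting research and Blinded assessor will not have access to which groups patients are enrolled in".

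**Order of steps.** "Once patients consent to enroll in the study, they will receive the next envelope in sequence in the group of 4". Under Inclusion / Exclusion Criteria, "we will confirm the diagnosis at the first therapy visit", but only where the referring diagnosis is something other than lateral epicondylitis or tennis elbow. Data Collection has baseline data gathered once consent is signed. The Blinding section has grip recorded by the treating therapist, who knows the arm.

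**The concern.** Patients and therapists know the treatment and the primary outcome is self-reported, so concealment up to the moment of enrolment is one of the main protections the design still has. If someone who enrols can learn the next assignment, a patient can be encouraged, deferred or judged ineligible with the arm in mind. The groups then differ in prognosis, and with 44 patients an analysis cannot reliably repair imbalance on factors that were not measured.

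The second route is through baseline. All the main comparisons are changes from baseline. A baseline taken after the arm is known can be influenced by that knowledge, and the shift passes directly into the change score. The route is most direct for grip, which an unblinded therapist measures. It is also open for PRTEE and NPRS if the patient already knows the arm when answering.

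**Working it through.** **1. The plan's own count.** Two sites hold 4 blocks of 4 and one site holds 3 blocks of 4: 2 × 4 × 4 + 1 × 3 × 4 = 44 envelopes, or 22 per arm at 1:1. This agrees with the stated total.

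**2. Custody of the list, statements side by side.**

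| Statement | Section | Consequence |
|---|---|---|
| Treating therapist compares the envelope number with the list | Randomization/Allocation | Therapist has some use of the list |
| Primary investigator holds the list in confidence | Randomization/Allocation | Therapist should not have it |
| Site therapists may obtain consent | Recruitment/Enrollment; Randomization/Allocation | A therapist can be an enroller |
| A master list is kept by the researcher who enrols or consents | Confidentiality of Data | Unclear whether this is the subject-number list or the allocation list |
| Enrolling or consenting researcher cannot see groups | Confidentiality of Data | Cannot hold for a therapist who both consents and treats |

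No sentence requires the consenting and treating therapist to be different people. Brief Design Description makes overlap plausible: "At each site, 1 therapist will undergo a 2 hour standardized training session on delivery of treatment and data collection". It does not prove overlap, since the Device section expects other therapists to take part.

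**3. Order of steps.** Consent triggers the envelope, and consent also opens baseline data collection. Neither is placed before the other. Outcomes assessment has the PRTEE issued before the physical examination, which helps but does not place it before the envelope. Grip and 1RM are due at entry, again with no link to the envelope. Therapy Protocols describes 1RM estimation within the arm-specific treatment.

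**4. How many assignments could be anticipated.** This measures foreknowledge, not bias.

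- *List seen beforehand and next number known:* 44 of 44.
- *List not seen, but block size and all earlier assignments at the site known:* a 1:1 block of 4 has 6 possible sequences. Two of them (AABB, BBAA) fix the last two places and the other four fix only the last. Certain assignments per block = (2 × 2 + 4 × 1) / 6 = 1.33, or 33%. Over 11 blocks this is 14.7 of 44. Always guessing the under-represented arm is right with probability 1/2, 2/3, 2/3 and 1 at the four places. The sum is 2.83 of 4, or 70.8%, and 11 × 2.83 gives about 31.2 of 44.
- *Neither known:* 50%, or 22 of 44.

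The documents do not say which case applies. They do not say that therapists are told the block size, or that the number inside an envelope matches its outer sequence number.

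**The case against.** The safeguards are real. The sequence comes from web-based software, and the envelopes are opaque, sequentially numbered and taken out only after enrolment. The look-up described also comes after consent, so the look-up itself does not break concealment. Only earlier sight of the list would, and no such access is described.

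A reader might infer that the list sits at each clinic. The documents do not say so: only the envelopes are sent to the clinics, and the list is assigned to the primary investigator. A reader might also infer that the envelope holds nothing but a code. The sentence on reporting to the primary investigator can be read as placing allocation and PID inside it, so the text is ambiguous. Nor do the documents say that one therapist consents, confirms the diagnosis, stores envelopes and decodes them. Storage falls to the directing therapist, decoding to the treating therapist, and first contact to a consent team.

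On baseline, PRTEE and NPRS are self-entered and the treating therapists are blinded to the results. Unblinded grip testing is disclosed and affects secondary outcomes only.

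All of this stands, and it limits the claim. It does not resolve the conflict over the list, supply a one-at-a-time release, or put eligibility and baseline before the reveal. The disclosure about grip concerns knowledge of treatment during assessment, not the timing of the baseline measurement.

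**Conclusion.** The point holds in this form: as written, concealment cannot be relied on. The two sections disagree on who may use the list, therapists who may enrol are told to consult it, and the order of consent, eligibility, baseline and reveal is left open.

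A reader might go further and conclude that allocation is unconcealed and all 44 assignments are foreseeable. That needs sight of the list before the next enrolment and a way to infer the number in the next envelope. The documents establish neither.

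A reader might also put the bias in points: a shift of d in favour of one arm and d against the other gives a bias of 2d. The documents supply no d, and the formula assumes equal steering in both directions across all patients. The size of any bias cannot be derived from the plan.

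The block-guessing figures assume knowledge of the block size and of earlier assignments. That route does not depend on the list, and settling custody of the list would not close it.

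**What to change.** In Randomization/Allocation:

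- Remove the therapist's comparison with the list. Put the group and PID inside each sealed, opaque, sequentially numbered envelope, or use a REDCap randomisation form.
- Name a person who neither enrols nor treats to hold the sequence.
- State that the envelope is opened, or the form released, only after these are recorded: consent, eligibility (including the first-visit check for non-specific diagnoses), and baseline PRTEE, NPRS, grip and 1RM. Recording on paper should count, because the Blinding section allows paper forms to be entered into REDCap later.

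In Confidentiality of Data, say which master list is meant, who holds it and who may see groups, so that the section agrees with Randomization/Allocation when a therapist takes consent.

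The cost is re-stuffing 44 envelopes or building one form, plus a fixed order of steps at the first visit, which is a small change to clinic workflow. No extra patients are needed.
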